#### 3.5.3.2. ECG of Special Clinical Concerns

Individual participants' ECG outlined in Table 4 of special clinical concern, which align with the Pfizer standard criteria, will be summarized by treatment, as part of standard safety-related outputs.

**Table 4 ECG QT and QTc Interval Criteria to be Monitored**

Degree of Prolongation	QTcF Interval Prolongation (msec)			Uncorrected QT Interval (msec)
	Mild (msec)	Moderate (msec)	Severe (msec)	
Absolute value	>450-480	>480-500	>500	>500

**Table 4 ECG QT and QTc Interval Criteria to be Monitored**

Degree of Prolongation	QTcF Interval Prolongation (msec)			Uncorrected QT Interval (msec)
	Mild (msec)	Moderate (msec)	Severe (msec)	
Increase from baseline		30-60	>60	

Note: For purposes of reporting study-level results, QTcF interval will be derived using Fridericia's heart rate correction formula (see below) applied to databased QT interval, and RR interval.

QTc not otherwise specified as captured in CRF will be only listed. Summary outputs will summarize only programmatically derived QTcF.

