### 8.2.3. Electrocardiograms

Standard single 12-lead ECGs utilizing limb leads (with a 10 second rhythm strip) should be collected at times specified in SoA – [Table 1](#) using an ECG machine that automatically calculates the RR interval (or heart rate) and measures PR, QT, and QTc intervals and QRS complex. Alternative lead placement methodology using torso leads (eg, Mason-Likar) is **not** recommended given the potential risk of discrepancies with ECGs acquired using standard limb lead placement.

- All scheduled 12-lead ECGs should be performed after the participant has rested quietly for **≥10 minutes** in a supine position;
- Starting at Day 1/Visit 4, if a machine-read QTc value is prolonged, as defined in [Appendix 10.7](#), repeat measurements may not be necessary if a qualified physician's interpretation determines that the QTc values are in the acceptable range;
  - Assessment of whether prolonged QTc interval meets criteria as defined in [Appendix 10.7](#), must assess QTc interval using **only** the Fridericia's correction (ie, QTcF) **either** as reported by the 12-lead ECG machine **or** QTcF derived using Sponsor-provided tool and reported QT and RR intervals;
  - In some cases, it may be appropriate to repeat abnormal 12-lead ECGs to rule out improper lead placement as contributing to the ECG abnormality; **as much as practically, possible**, it is important that leads be placed in the same positions each time in order to achieve precise ECG recordings.

Additional ECG values of potential clinical concern are listed in [Appendix 10.7](#).

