#### **9.4.5.2. Electrocardiogram Analyses**

Changes from baseline for the ECG parameters QT interval, heart rate, QTcF interval, PR interval, and QRS interval will be summarized by treatment and time. QTcF will be derived using Fridericia's heart rate correction formula. The number (%) of participants with maximum increases from baseline will be tabulated by treatment as defined in the SAP. Numbers and percentages of participants meeting the categorical criteria will be provided and individual values listed in the study report. No formal inferential statistics will be applied to the ECG data.

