**QTcF (ie, Fridericia's heart rate correction formula) is:**

$$\text{QTcF (msec)} = \text{QT(msec)} / (\text{RR, in msec})^{(1/3)}$$

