### **6.6.3. Electrocardiogram Analyses**

ECGs will be summarized by visits. Categorical summary of ECGs will be presented according to Pfizer standards (note that baseline is defined as in [Section 3.4](#) in relation to actual treatment).

Changes from baseline for the ECG parameters QT interval, RR interval, calculated QTcF interval (using QT and RR interval), PR interval, and QRS interval will be summarized by treatment and time. QTcF will be derived using Fridericia's correction formula. The number (%) of participants with maximum increases from baseline will be tabulated by treatment as defined in the [Section 5.2.3](#). Numbers and percentages of participants meeting the categorical criteria will be provided and individual values listed in the study report.

No formal inferential statistics will be applied to the ECG data.

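### The SAP's QTcF formula takes RR in msec without dividing by 1000, so every derived QTcF would be a tenth of its true size and Table 4's five QTcF categories would in practice be empty

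*SAP*

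**What the plan says.** SAP Section 3.5.3.2 (ECG of Special Clinical Concerns) sets out Table 4, which has five QTcF categories in msec. Three are absolute (>450-480, >480-500, >500) and two are increases from baseline (30-60, >60). A separate column, "Uncorrected QT Interval (msec"), flags values above 500.

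The note to Table 4 says that for study-level results QTcF is obtained by Fridericia's "heart rate correction formula (see below) applied to databased QT interval, and RR interval". QTc captured on the CRF is only listed, and the note adds: "Summary outputs will summarize only programmatically derived QTcF".

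The formula follows under the label "QTcF (ie, Fridericia's heart rate correction formula) is". It defines QTcF (msec) as QT (msec) divided by the cube root of RR, with the unit of RR spelled out as msec. Nothing divides RR by 1000.

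The derived value is used in SAP Section 6.6.3, where "calculated QTcF interval (using QT and RR interval), PR interval, and QRS interval will be summarized by treatment and time". Protocol Section 9.4.5.2 also names Fridericia's correction and defers to the SAP for the categories: "The number (%) of participants with maximum increases from baseline will be tabulated by treatment as defined in the SAP". Neither section gives a unit for RR.

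**The concern.** A heart-rate correction should leave QT unchanged at a reference rate and keep QTcF on the same scale as QT. The SAP's formula does neither. At 60 beats per minute, where RR is 1000 msec, it divides QT by 10. The results cannot be compared with Table 4's cut-offs, or with the Protocol's own 480 msec thresholds (exclusion criterion 15 in Section 5.2, and Appendix 7 in Section 10.7).

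What is at stake is the descriptive ECG safety reporting. SAP Section 6.2.2 places the categorical ECG summary under the secondary safety and tolerability endpoint. Coded literally, the QTcF part of that summary would show no prolongation in any arm whatever the data. Read on its own, an empty table looks like a clean result. The uncorrected QT column does not fill the gap, because at a faster heart rate QTcF can exceed 500 msec while QT stays below it.

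**Working it through.** The documents contain no worked QTcF value to reproduce, so the check evaluates the formula directly. The formula and the Table 4 cut-offs come from SAP Section 3.5.3.2. The QT and RR values below are illustrative assumptions, not figures from the documents.

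**1. Size of the scale error**

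- As written: QTcF = QT / (RR in msec)^(1/3)
- Rescaled: QTcF = QT / (RR in msec / 1000)^(1/3)
- Rescaled divided by as written = 1000^(1/3) = 10

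The factor is exactly 10 for every QT and RR. On a grid of QT 360-550 msec and heart rates of 40-120 beats per minute, the formula as written gives values from 31.4 to 69.3.

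**2. Individual values**

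| QT (msec) | RR (msec) | QTcF as written | QTcF rescaled | Table 4 absolute category if rescaled |
|---|---|---|---|---|
| 400 | 1000 | 400/10 = 40.0 | 400.0 | none |
| 430 | 800 | 46.3 | 463.2 | >450-480 |
| 460 | 750 | 50.6 | 506.3 | >500 |
| 480 | 850 | 50.7 | 506.7 | >500 |

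As written, none of the four meets any absolute QTcF category.

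**3. A baseline and on-treatment pair**

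Take QT 400 at RR 1000 at baseline and QT 480 at RR 850 on treatment.

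- Rescaled: 506.7 - 400.0 = 106.7 msec. This meets >500 and an increase >60.
- As written: 50.7 - 40.0 = 10.7. This meets no QTcF category.
- Uncorrected QT of 480 does not exceed 500, so that column misses the participant too.

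**4. What it would take to reach a category as written**

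- An absolute value above 450 needs QT > 450 × RR^(1/3): 3,795 msec at RR 600, 4,500 msec at RR 1000 and 4,782 msec at RR 1200.
- At fixed RR, an increase of 30 needs a QT rise of 30 × RR^(1/3): 253 msec at RR 600 and 319 msec at RR 1200.
- At fixed RR, an increase of 60 needs a QT rise of 506 msec at RR 600 and 638 msec at RR 1200.

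Such values are unrealistic, so all five categories would in practice be empty.

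**5. Is it corrected elsewhere?**

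No. SAP Section 6.6.3 and Protocol Section 9.4.5.2 name the method without units. The version 2 entry in the SAP version history lists only changes for derived non-HDL-C.

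**The case against.** The strongest reply is that this is a notation slip with a plain intent. Both documents name Fridericia's correction, Table 4's cut-offs are in the hundreds of msec, and ECG outputs follow sponsor standards. A standard macro would probably compute QTcF correctly, and a reviewer should notice QTcF near 40 beside QT near 400. The values can be rebuilt from the databased QT and RR. That makes lasting harm unlikely. It does not make the specification right: a correct program would contradict the SAP, and a program validated against the SAP would be wrong.

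A second reply is that no participant-level or mid-study decision is shown to depend on the formula. That is so. Under Protocol Section 8.2.3, site assessment uses the machine's QTcF or "QTcF derived using Sponsor-provided tool and reported QT and RR intervals". Clinically significant ECG findings reach the AE record through investigator judgment (Protocol Section 10.3.1). The list of outputs for the Internal Review Committee in SAP Section 7.1.1 names no ECG item. What is exposed is end-of-study descriptive reporting, with no inferential statistics planned for ECG.

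Third, the 106.7 msec rise in the worked pair is large. The Protocol excludes QTc above 480 msec at entry and reports no clinically significant effect on conduction intervals in earlier studies (Section 2.2.1). With about 18 participants per group, the upper categories may be sparse even when computed correctly. But the factor of 10 does not depend on the example, and the milder case (QT 430 at RR 800) also drops out of its category.

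Finally, the equation was read from a PDF, so a misread cannot be wholly excluded. It is unlikely, because the unit is written out in words.

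**Conclusion.** The concern holds. As written, the formula returns exactly one tenth of QTcF. Following it would empty all five QTcF categories in Table 4 and shrink the by-visit QTcF values and changes tenfold. The consequence is conditional on the line being programmed literally; the documents do not show how the ECG programs were written. The conclusion does not rest on an outside definition of the correction: a result of QT/10 at RR 1000 msec cannot fit the SAP's own cut-offs.

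Not affected are the uncorrected QT >500 category, the listed CRF QTc, the QT, RR, PR and QRS summaries, site-level QTcF assessment and AE reporting, and the liver fat and triglyceride analyses. This is a specification error that should be fixed. It does not threaten the trial's main results.

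**What to change.** In SAP Section 3.5.3.2, replace the formula with: QTcF (msec) = QT (msec) / (RR in msec / 1000)^(1/3).

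If ECG programs already exist, check them against the corrected line; QT 400 at RR 1000 msec must return 400.

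The cost is one line of SAP text and a short program check. It needs no new data and no change to Table 4, the Protocol thresholds or any participant-level procedure.

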**QTcF (ie, Fridericia's heart rate correction formula) is:**

$$\text{QTcF (msec)} = \text{QT(msec)} / (\text{RR, in msec})^{(1/3)}$$

### 3.5.3.3. Background Medications of Special Interest

Across the many background medications being taken by the population enrolled, the number/proportion of participants using (and proportion needing changes in) selected medications of special interest will be summarized. These include

- Agents for glycemic control (see list in Protocol section 6.5.1)
- Agents for lipid control (see list in Protocol section 6.5.2)
- Agents for blood pressure control (see list in Protocol section 6.5.3)

The number of participants using glycemic control agents, lipid-modifying agents medication, and agents for BP control will be summarized by treatment as well.

For each category of medication (ie Glycemic, Lipid, and BP), the number of participants receiving 0, 1, 2, or 3 medications will also be tabulated by treatment.

Given the relatively short duration of the double-blind, double-dummy dosing in this study, if changes in background medications related to glycemic control, lipid control, or blood pressure are reported/observed, they will be summarized as follows, at any time after Day 1 and up to the last dose of study drug (ie, Week 6 or premature discontinuation) whichever is first –

- Dose increase and decrease in concomitant medication for glycemic control (see list in Protocol section 6.5.1),
- Dose increase and decrease in concomitant lipid-modifying medications (see list in Protocol section 6.5.2),
- Dose increase and decrease in concomitant blood pressure management medications (see list in Protocol section 6.5.3).

### 3.5.3.4. Platelet Count

Percent and absolute change from baseline in platelet count over time will be the endpoint of interest. Both endpoints will be analyzed as described in [Section 5.2.5](#).

Baseline is defined as described in [Section 3.4](#) .

### 3.5.3.5. Estimated Glomerular Filtration Rate

The estimated glomerular filtration rate (eGFR) at each time point defined in the Schedule of Activities will be calculated using cystatin-C as follows:

If cystatin-C > 0.8 mg/L:

$$\text{eGFR} = 133 * [(\text{cystatin} - \text{C})/0.8]^{-1.328} * 0.996^{\text{Age}} * 0.932 \text{ (if Female)}$$

If cystatin-C ≤ 0.8 mg/L:

$$\text{eGFR} = 133 * [(\text{cystatin} - \text{C})/0.8]^{-0.499} * 0.996^{\text{Age}} * 0.932 \text{ (if Female)}$$

Where eGFR unit is mL/min/1.73 m^2,

Age is subject's age at screening in years,

(cystatin-C) is cystatin-C concentration in mg/dL.

The change from baseline in eGFR over time will be the endpoint of interest and will be analyzed as described in [Section 5.2.5](#).

Baseline is defined as described in [Section 3.4](#).

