### **Diagnostic Assessments:**

14. Results as reported by Sponsor-identified central laboratory, at PreQ **and** SCR, as below with a single repeat of **any** of these parameters permitted to assess eligibility, if needed, at **each** of these 2 visits:
  - ALT <ULN **or** >5x ULN;
  - AST >5x ULN;
  - Alkaline phosphatase (ALP) >2x ULN;
  - Total bilirubin >ULN and direct bilirubin >ULN;
  - **Note:** Participants with a history of Gilbert syndrome would be eligible for this study provided direct bilirubin level is  $\leq$  ULN, and hemoglobin and reticulocyte count are within the reference range of the Sponsor-identified central laboratory;
  - **Note:** If there is a >50% variability between the PreQ (**or** PreQ repeat, if performed) and SCR results for ALT, AST, **or** alkaline phosphatase **or** total bilirubin is > ULN, these LFTs must be repeated 1 additional time,  $\geq$ 2 weeks after SCR, with the variability between the PreQ (**or** PreQ repeat, if performed) and the 1 additional measurement confirmed to be  $\leq$ 50% for ALT, AST, **and** alkaline phosphatase, **and** total bilirubin  $\leq$  ULN, **and** within the parameters above to confirm eligibility, as reported by the Sponsor-identified central laboratory, **prior to** progressing to the Run-In/Visit 2;
  - HbA1C >9% (75 mmol/mol), as assessed using NGSP certified method and standardized to DCCT assay;
  - Fasting Plasma Glucose >270 mg/dL (15 mmol/L);

- Fasting serum triglycerides >400 mg/dL (4.5 mmol/L);
- Platelet count < LLN;
- INR  $\geq$ 1.3;
- Albumin < LLN;
- eGFR (using CKD-EPI-Cystatin-C) of <30 ml/min/1.73 m^2;
- A positive urine drug test for illicit drugs (with this 1 assessment **not** permitted to be repeated at *each* visit to confirm eligibility).

15. At PreQ *or* SCR, supine 12-lead ECG demonstrating QTc interval >480 msec *or* QRS interval >120 msec;

- If QTc interval exceeds 480 msec or QRS interval exceed 120 msec, the 12-lead ECG should be repeated *twice* (on the same *or* different day) and the *average of three* QTc/QRS intervals used to determine eligibility;
  - **Note:** if ***uncorrected*** QT interval is >480 msec, this interval must be rate-corrected using the Fridericia method, with the resulting QTcF used for decision making and reporting.

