**Table 6. All Planned Protocol Required Safety-Related Laboratory Tests and Exploratory Biomarkers in Study C3711005**

Hematology	Chemistry	Urinalysis
– Hemoglobin	– BUN	– pH
– Hematocrit	– Creatinine	– Glucose (qual)
– RBC count	– Cystatin-C (and eGFR using CKD-Epi-Cystatin-C)	– Protein (qual)
– Reticulocyte count (Abs)	– Plasma Glucose (fasting)	– Blood (qual)
– MCV	– Calcium	– Ketones
– MCH	– Sodium	– Nitrites
– MCHC	– Potassium	– Leukocyte esterase
– Platelet count	– Chloride	– Urobilinogen
– WBC count	– Total CO 2 (bicarbonate)	– Urine bilirubin
– Total neutrophils (Abs)	– AST (SGOT)	– Microscopy a
– Eosinophils (Abs)	– ALT (SGPT)	
– Monocytes (Abs)	– Total bilirubin	
– Basophils (Abs)	– Alkaline phosphatase	
– Lymphocytes (Abs)	– GGT	
	– Direct (conjugated) bilirubin	
	– Indirect (unconjugated) bilirubin	
	– Total bile acids	
	– Creatine Kinase	
	– Uric acid	
	– Albumin	
	– Total protein	

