## 1. VERSION HISTORY

**Table 1. Summary of Changes**

Version/ Date	Associated Protocol Amendment	Rationale	Specific Changes
1 / 11-Aug-2020	Original protocol dated 27-Mar-2020 + associated PACL dated 01-Jul-2020	N/A	N/A
2 / 16-Jun-2021	Original protocol dated 27-Mar-2020 + associated PACL dated 01-Jul-2020 + associated PACL dated 22-Jan-2021	Per request from IRC as part of 1 st safety review (May2021) to include derived non-HDL-C	

• Sections 2.1, 3.3.4, 6.3.4, and 7.1.1 were modified to include derived non-HDL-C as endpoint along with summarization, and analysis.

• Appendix 4 was modified to include non-HDL-C acronym definition.

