#### 6.6.4.2. Estimated Glomerular Filtration Rate

Raw data, and changes from baseline will be summarized by treatment, and week as described in [Section 5.2.2](#).

The statistical analysis will be performed using the change from baseline as described in [Section 5.2.5\\_Ref41484348](#).

- Statistical Outputs:
  - ✓ The LSMeans estimates, and 80% confidence interval for each treatment at each time-point,
  - ✓ Difference between the LSMeans for active treatment against placebo and the corresponding 80% confidence interval will be presented at each time point.
  - ✓ Summary tables reporting MMRM outputs will include the number of participants included in the analysis.
- Figures from statistical outputs
  - ✓ Line Plot of LSMeans estimates and 80% confidence interval over time,
  - ✓ Line Plot of placebo adjusted LSMeans and 80% confidence interval over time.

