#### **Study conduct and Baseline characteristics of Population Randomized:**

- Study conduct issues (e.g., enrollment status, currentness of the database, time between randomization and first treatment, eligibility violations)
- Participant evaluation groups
- Demographic and other baseline characteristics

**Safety Data:** The Committee will monitor certain specific safety-related laboratory parameters, vital sign parameters, and treatment-emergent adverse events (TEAEs) as well as serious adverse events (SAEs including death) listings in an unblinded manner for overall frequency of events. To do so, the listings which will be provided include:

- TEAEs (and SAEs) leading to temporary discontinuation of dosing;
- TEAEs (and SAEs) leading to permanent discontinuation and withdrawal;
- The listing of individual TEAEs and SAEs;
- All instances of hyperglycemia, or platelet reduction, or hypertriglyceridemia leading to permanent withdrawal;
- Listing of Treatment emergent adverse events (TEAEs) as defined in section 6.6 of this SAP;
- Listings of SAEs/deaths and narratives requested from the safety database (ie, ARGUS or similar)
- eGFR values and laboratory parameters outlined in Table 2 of this SAP represent the minimum list of parameters which will be listed and provided to the committee.
- This list may be expanded depending on team blinded review.

The Committee will receive the distribution of participants over time whose values cross the boundaries (ie Flag and Alert levels separately) for each of the parameters included in Table 2 of this SAP.

Percent change from baseline in fasting lipid parameters (ie triglycerides, total cholesterol, direct LDL-C, VLDL, HDL-C, and derived non-HDL-C), fasting apolipoproteins (ie ApoA1, ApoBtotal, ApoB100, ApoB48, ApoC3, and ApoE), liver function parameters (ie ALT, AST, Total Bilirubin, GGT, and Alkaline Phosphatase), eGFR, and will be provided for review.

Change from baseline in glycemic parameters (ie HbA1c, FPI and FPG) will be provided for review as well.

The following graphical representations will be provided:

- Box and whiskers plots of percent change from baseline for parameters in Table 2, eGFR, fasting lipid parameters (see list above), fasting apolipoproteins (see list above), and liver function test.
- Box and whiskers plots of changes from baseline for glycemic parameters (see list above):

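### SAP 3.5.3.5 gives cystatin-C in mg/L for choosing the branch but mg/dL for the value entered; following the mg/dL line makes derived eGFR at least 3-fold too high

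*SAP*

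**What the plan says.** SAP 3.5.3.5 has two branches, headed "If cystatin-C > 0.8 mg/L" and "If cystatin-C ≤ 0.8 mg/L". Each multiplies 133 by a power of cystatin-C divided by 0.8, by 0.996 to the power of age, and by 0.932 for women. The exponent is -1.328 in the upper branch and -0.499 in the lower. The legend below the equations then reads "cystatin-C) is cystatin-C concentration in mg/dL".

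The derived value is used in two places:

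- **SAP 6.6.4.2**, final analysis: "The statistical analysis will be performed using the change from baseline as described in" Section 5.2.5, that is, an MMRM on absolute change.
- **SAP 7.1.1**, IRC outputs: listed eGFR values, and "Box and whiskers plots of percent change from baseline for parameters in Table 2, eGFR, fasting lipid parameters".

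Protocol Table 6 lists "Cystatin-C (and eGFR using CKD-Epi-Cystatin-C") among the chemistry tests without a unit. Cystatin-C does not appear in SAP Table 2. Neither document gives its unit anywhere else.

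**The concern.** The same 0.8 is both the branch point and the divisor, so one unit must serve both. As written, the section uses two units that differ 10-fold. A programmer who follows the legend enters a number one tenth of the size the equation expects. Because the exponents are negative, eGFR then comes out too high, in the direction that hides renal impairment.

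This measure carries weight in the trial. Protocol 2.2.1 reports that DGAT2i raises serum creatinine through OCT2/MATE inhibition, and relies on cystatin-C eGFR to show that renal function itself is unchanged. Creatinine is therefore a poor fallback if the cystatin-C derivation is wrong.

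**Working it through.** The documents state no eGFR result, so there is no figure to reproduce. The check evaluates the SAP's equation under each possible reading.

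**Inputs.** Constants 133, 0.8, -1.328, -0.499, 0.996 and 0.932 are from SAP 3.5.3.5. Ages 18 to 75 are from protocol 5.1, and the eGFR limit of 30 from protocol 5.2, criterion 14. The illustrative man aged 55 and the cystatin-C values are assumptions. Let c be cystatin-C in mg/L; the same sample in mg/dL is c/10.

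**Which unit fits.** In mg/L, c/0.8 = 1 at the branch point, so both powers equal 1 and both branches give 133 × 0.996^55 = 106.7. If 0.08 mg/dL is inserted there, the lower branch gives 106.7 × 10^0.499 = 337 and the upper gives 106.7 × 10^1.328 = 2,270. That is a jump of 10^(1.328 - 0.499) = 10^0.829 = 6.7-fold. Only mg/L makes the curve continuous.

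**Inflation.** Age and sex cancel in the ratio of wrong to right.

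- At or below 0.8 mg/L, either reading: 10^0.499 = 3.16.
- Above 0.8 mg/L, branch chosen in mg/L and mg/dL entered (mixed reading): 10^1.328 = 21.28.
- Above 0.8 mg/L, mg/dL throughout: the upper branch now starts only at 8 mg/L, so the lower branch is used and the ratio is 3.16 × (c/0.8)^0.829. This gives 3.80 at 1.0, 5.31 at 1.5, 6.74 at 2.0 and 7.02 at 2.1 mg/L.

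The smallest ratio over 0.3 to 10 mg/L is 3.16 under both readings, so at least 3-fold is a true lower bound.

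**At the protocol's limit.** Solving the upper branch for a true eGFR of 30 gives c from 1.86 mg/L (woman aged 75) to 2.33 mg/L (man aged 18). With mg/dL throughout, these people would show 190 to 229. Under the mixed reading all would show 30 × 21.28 = 638.

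**Change from baseline, man aged 55** (absolute change in mL/min/1.73 m², then percent):

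| Cystatin-C, mg/L | Correct (mg/L) | mg/dL throughout | Mixed |
|---|---|---|---|
| 1.0 to 1.2 | 79.3 to 62.3: -17 (-21.5%) | 301.1 to 274.9: -26 (-8.7%) | 1,688 to 1,325: -363 (-21.5%) |
| 1.0 to 2.0 | 79.3 to 31.6: -48 (-60%) | 301.1 to 213.1: -88 (-29%) | 1,688 to 672: -1,016 (-60%) |
| 0.79 to 0.85 | 107.4 to 98.4: -9 | 338.7 to 326.6: -12 | 338.7 to 2,095: +1,756 |

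With mg/dL throughout, the two planned outputs err in opposite directions. Absolute falls are enlarged (by at least 1.19-fold over 0.4 to 4 mg/L), while percent falls above 0.8 mg/L are muted. Under the mixed reading, percent change is right only when both visits lie in the same branch, and a fall in function that crosses 0.8 mg/L appears as a large rise.

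**The case against.** The strongest reply is that this is a one-word slip with an obvious answer. Two of the three unit statements say mg/L, the equation is named in the protocol, and its source is in both reference lists. If the laboratory sends mg/L and the number is used as received, nothing goes wrong. An error needs a mg/dL transfer used unconverted, or a deliberate division by 10. Mixed-reading values in the hundreds or thousands would probably be noticed. eGFR has no flag or alert level in SAP Table 2 and is not among the listed primary, secondary or tertiary endpoints. The IRC reviews involve no formal analysis.

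Most of this stands, and it limits the weight of the point: the harm is conditional, and the mixed-reading figures are the least likely to pass unseen. It does not remove the contradiction. A cited source does not correct the SAP's own text. The mg/dL-throughout reading is harder to catch, since it gives a smooth curve with changes in the right direction, although a level near 301 for a man of 55 at 1.0 mg/L should still raise a question.

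Whether IRC outputs were affected is unknown. SAP Table 1 attributes version 2 to a request at the IRC's first "safety review (May2021) to include derived non-HDL-C" and lists no change to 3.5.3.5. It is an inference, not a documented fact, that the same line stood at that review; nothing shows how the eGFR outputs were derived.

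**Conclusion.** The concern holds: the derivation rule is wrong as written. The unit in the legend contradicts both branch conditions and the divisor, and the equation is continuous only in mg/L. If the legend is followed, eGFR is overstated at least 3.16-fold in everyone, by more above 0.8 mg/L, and change from baseline is distorted in both the MMRM and the IRC displays. The fold factors do not depend on age or sex; the worked changes assume a man aged 55 and chosen cystatin-C values.

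The size is conditional on the programming, which the documents do not show. Eligibility is not affected, because criterion 14 ("eGFR (using CKD-EPI-Cystatin-C) of <30 ml/min/1.73" m²) uses results reported by the central laboratory. The primary endpoint and the sample size are not affected either. This should be fixed, but it does not threaten the trial's main conclusion.

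**What to change.** In the legend of SAP 3.5.3.5, change the cystatin-C unit to mg/L. State the unit in which the central laboratory transfers cystatin-C, and add a conversion if it is not mg/L. Compare derived eGFR with the laboratory-reported eGFR in protocol Table 6, where available, and include any IRC outputs already produced. A ratio near 1 would clear the matter; a ratio of 3 or more would show that the mg/dL line had been followed.

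The cost is one word in the SAP, one check of the transfer unit and one comparison. No new data are needed.
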